### Environmental Exposure(s)

**PaGER Environmental Exposures Questionnaire – Short Version (EEQs), [2-5 minutes].** The EEQs is a 15-item questionnaire assessing environmental exposures in Parkinson's disease. Originally developed as part of the NW PADRECC's "*Parkinson's Genetic Research Study (PaGER)*". This questionnaire assesses the life-time exposure to tobacco, non-steroidal anti-inflammatory drugs (NSAIDs), and caffeine. These factors may contribute to the progression of PD overtime [68].

### Cognition

**Montreal Cognitive Assessment (MoCA); [15-20 minutes].** The MoCA is a short cognitive screening test designed to assist health care professionals for the detection of mild cognitive impairment. The MoCA assesses cognitive function across a variety of domains, such as visuospatial /executive functioning, naming (animals), memory, attention, language, abstraction, delayed recall, and orientation. The MoCA is scored on a 0 to 30 scale, with lower numbers indicating more cognitive impairment. A point is added to the MoCA if the subject's education high school or less (12 years or less education). Scores ranging from 26 - 30 are normal, 18 - 26 mild impairment, 10 - 17 moderate impairment, and less than 10 severe cognitive impairment. The MoCA is a well established screening test in Parkinson's disease patients and is able to discriminate between mild cognitive impairment and dementia [66, 67].

**Adverse Events** (as recommended by the NINDS Common Data Elements for research reporting). To document medical events that occur to a subject once enrolled. AEs are the construct through which the safety of an intervention is recorded and assessed during a study. All AEs, both serious and non-serious, regardless of relationship to the study intervention, will be recorded on the AE case report form (CRF). AE data will be collected from the time the informed consent form is signed through the duration of the clinical investigation. Typical AE descriptors include event start date, severity, relatedness, outcome, and an indication of whether the event is serious. We will use Common Terminology Criteria for Adverse Events (CTCAE). Local non-serious AEs will be recorded on the CRFs and handled at the local site. Serious AEs will be reported within guidelines to the DSMB, FDA, and IRBs.

**pERK1/2 Levels.** Immunodetection of pERK with antibody against the phosphorylated forms of Tyrosine202 and 204 of ERK1/2 (AlexaFluor488 BD Biosciences) will occur in lymphocytes isolated from whole blood using flow cytometry. Human peripheral blood mononuclear cells (PBMC) will be isolated using a Ficoll-Paque standard protocol. We will stain CD3 (T lymphocytes) and CD20 (B lymphocytes). Data will be expressed as percentage of pERK cells compared with ERK in a fixed volume of cell preparation.

**Plasma Levodopa Measurements.** As a quality control measure, plasma levodopa levels will be measured at each 11:00 am directly before the levodopa infusion is discontinued. Blood draw will consist of one 6mL lavender top tube that is centrifuged at 3,000 RPG at -4° C for 15 minutes. Plasma will be aliquoted into two 1.5 mL tubes. Plasma samples will be stored at -80C and analyzed using liquid chromatography mass spectrometry at [name] laboratory (OHSU). Batch analysis will occur on the first tube (tube 01) after 30 samples have been collected. At the end of the study, the second tube will be destroyed or placed in the *Neurological Disorders Repository (NDR)* per the participant's wishes.

**Framingham Risk Score (FRS).** [5 min]. The Framingham Risk Score is a gender-specific algorithm used to estimate the 10- year risk of cardiovascular disease (CVD) risk, cerebrovascular events, peripheral artery disease and heart failure.(53) The algorithm uses age, gender, HDL-C levels, total cholesterol levels, systolic blood pressure, smoking status, diabetes status, and family history of CVD in first degree relative before age 60 to calculate 10-year CVD risk. Using the data from the National Heart, Lung, and Blood Institute's Framingham Heart Study based on predominantly Caucasian population in Massachusetts, USA, risk estimates are divided into risk categories of low (0-10% risk), moderate (10-20% risk), and high risk (20% or more).

#### **Procedures:**

Subjects will attend one screening visit and one day patient visit within 3 months of the screening visit. Subjects will be admitted to the day patient in research unit for an intravenous LD dose challenge to accurately determine how much LID they express. LID measurements will be repeated over several hours during the testing day to generate their LID AUC (described below, See

Table 3).

Table 3. Study Procedures

		Visit Procedures		
	Study Visit	Time Interval	VAPORHCS	VAPUGHCS/OHSU
In-Person	Screening (Outpatient)	0	Consent Form/HIPAA Authorization, Inclusion/Exclusion Criteria Parkinson's Assessment/Exams MoCA Vital Signs, ECG, Pregnancy Test (if applicable); Past Medical History; Physical Exam Blood draw (HDL-C/FRS)	Consent Form/ HIPAA Authorization, Inclusion/Exclusion Criteria MoCA Neurological Exam Vital Signs, ECG, Pregnancy Test (if applicable)
			2 hours	1 hour
Virtual	Consent	-1	Consent Form/HIPAA Authorization	Consent Form/ HIPAA Authorization
	Screening	0	Inclusion/Exclusion Criteria MoCA Past Medical History	Inclusion/Exclusion Criteria MoCA Past Medical History
			20 minutes	20 minutes
	@ Home	Visit - 1	Questionnaires (PDQ39, PDys-26, UPDRS I & II, UDysRS 1 & 2, NFOG)	Questionnaires (PDQ39, PDys-26, UPDRS I & II, UDysRS 1 & 2, NFOG)
	Visit Day patient (Portland OHSU OCTRI)	≤ 3 months	
*OHSU ICF/HIPAA Phone Consent (2-3 weeks prior)
 
*Parkinson's Assessment/Exams
 
*Past Medical History;
 
*Blood draw (HDL-C/FRS)
 
Hold all PD meds overnight before testing
 
Pregnancy test (if applicable)
 
IV LD Infusion
 
Inertial Sensors
 
LID Measurements: (Forceplate, mAIMS, UDysRS 3 & 4, PDys-26, UPDRS IV)
 
Parkinson's Measurements (Finger Tapping, UPDRS-III, TUG, CRST)
 
Blood Collection
 
6-9 hours
	
* italics indicate methods done for VAPUGHCS & OHSU participants at the Portland site
 

**Screening:**

**VAPORHCS:** After review and signing of the consent form and HIPAA Authorization with the subject, the inclusion/exclusion criteria will be reviewed. The UKBBPD Criteria will be completed. Inquiries about the subject's medical history, past statin and dopamine agonist use, and current medications will be made. Release of information forms will be completed for medication history stored outside of the VA system and/or outside of Care Everywhere. Baseline data collected on each subject will include: demographic information (such as race/ethnicity, handedness, year of diagnosis, etc), Parkinson's exam (UPDRS parts III and IV, Hoehn & Yahr, Swab & England Activities of Daily Living Scale), a short test of thinking and memory (MoCA), and a dyskinesia scale (PDys-26). Current daily dose of levodopa will be obtained. Additional baseline measurements will be gathered including vital signs, height, weight, and an ECG. A urine pregnancy test will be performed for women of childbearing age; the subject will not be able to continue in the study if pregnant. If the participant comes in fasting, a fasting blood draw will occur and be processed for cholesterol levels by the VA Pathology & Lab Department. Participants recruited from the general public and OHSU will be screened at the VAPORHCS. The OHSU consent/authorization form will be signed at this visit for the all-day visit and questionnaires will be mailed to the participant to complete the week of the day-patient visit.

**VAPUGHCS:** After review and signing of the consent form and HIPAA Authorization with the subject, the inclusion/exclusion criteria will be reviewed. The UKBBPD Criteria will be completed. Parkinson's exam (UPDRS parts III and IV, Hoehn & Yahr, Swab & England Activities of Daily Living Scale), a short test of thinking and memory (MoCA). Current daily dose of levodopa will be obtained. Additional baseline measurements will be gathered including allergies, vital signs, height, weight, and an ECG. A urine pregnancy test will be performed for women of childbearing age; the subject will not be able to continue in the study if pregnant. These procedures will be performed at the VA Puget Sound. The OHSU consent/authorization form and questionnaires will be mailed to the participant and phone consent will be obtained

**VIRTUAL VISIT:** The screening visit may be conducted virtually using VA Video Connect, WebEx, or HIPAA compliant Zoom. After receipt and review of the consent form and HIPAA Authorization by study staff, the screening visit will occur. The inclusion/exclusion criteria will be reviewed. The UKBBPD Criteria will be completed. Inquiries about the subject's medical history, past statin and dopamine agonist use, and current medications will be made. Release of information forms will be completed for medication history stored outside of the VA system and/or outside of Care Everywhere. Baseline data collected on each subject will include: demographic information (such as race/ethnicity, handedness, year of diagnosis, etc), Parkinson's exam (part IV, Hoehn & Yahr (if safe to do so), Swab & England Activities of Daily Living Scale), and a short test of thinking and memory (MoCA). Current daily dose of levodopa will be obtained. The OHSU consent/authorization form will be signed at this visit for the all-day visit and questionnaires will be mailed to the participant to complete the week of the day-patient visit.

**Day patient Visits**

All subjects from the recruitment sites (VAPORHCS, VAPUGHCS, and OHSU) will be seen for the day-patient visit at OHSU. Subjects will be required to either be driven to OHSU for this visit or to take alternative means of transportation (bus, tram, taxi, Lyft, or Uber). Subjects will be admitted to the OCTRI day patient unit at OHSU to begin procedures off PD medications. OCTRI is a dedicated research space for clinical studies at OHSU. The center is staffed by RNs for studies, provides nursing equipment (electrocardiographs, blood pressure monitors, etc.), contains a core laboratory, and provides bionutrition services. The core laboratory is adjacent to the clinical unit and provides laboratory support

to studies; performing a wide variety of assays and procedures. The bionutrition unit provides for the provision of research meals.

The subjects will hold their anti-parkinsonian medications while continuing to take their other non-Parkinsonian medications as prescribed, no further PD meds are taken until the end of data acquisition. The first data collection will begin the morning at 9:00AM in the practical OFF state. The subject will then be administered 1.5 mg/kg/hr of intravenous LD for 2 hours (9:30 AM-11:30 AM). The subject is also given oral carbidopa 25 mg at 9:00 AM, 11:00 AM and 13:00 PM to prevent nausea and prevent LD peripheral conversion to dopamine. The purpose of the L-dopa infusion is to create a therapeutic cycle or ON period (the ON period is considered the time the subject experiences the benefit of a dose of medication, with lessening of Parkinsonism. This is overwhelmingly also the time that LID is present). The subjective lessening of Parkinsonism symptoms will be verified by the UPDRS scores and the change in tapping scores. The outcome of interest will be how much LID is manifest during the period when LD is therapeutic. The constant rate infusion of LD produces a very reproducible rising concentration of plasma LD and is very different than the erratic absorption of oral LD.

Time (minutes):	30	5	25	5	5	10	10	5	5	5	5	5	25

aonly for those not screened at VAPORHCS or did not have blood draw at screen or completed the screening visit virtually

 will be repeated 3 times with the last instance being recorded

○ Indicates that this procedure will be performed at the last timed rating of the day (15:00/3:00 pm or when the participant turns “OFF”)

### Data Analysis.

The peak UDysRS total score will be used as the primary outcome measurement for LID as it is the accepted gold standard. We believe a more sensitive, precise, and reliable measure is our method of AUC calculations with IV levodopa, a full motor ON cycle and the use of an electronic measuring instrument (force plate). Therefore, additional outcome measurements will involve the computation of area under the curve for LID measurements of Modified Abnormal Involuntary Movement Scale (mAIMS) and the forceplate root mean square velocity in the anterior-posterior direction will be computed using the trapezoidal rule.

[figure not shown]
Primary analysis will follow a per protocol framework, using ordinary least-squares (OLS) regression to examine the difference between the groups (statin before LD, LD before statin, LD without statin) on LID outcome measures while correcting for LID related co-variates. Due to the nature of the retrospective selection, care will be taken to statistically account for potential confounders and modifiers on the relationship between LID and statin use. These will include, but not be limited to, age at onset of PD, gender, length of time taking L-dopa, total daily L-dopa dose, duration of disease, disease severity, and the presence of non PD factors related to a statin such as hypertension. In order to evaluate potential influences of secondary, cerebrovascular effects of indicated statin use on LID as an additional exploratory aim, we will also assess both duration (as a continuous linear variable) and dose of simvastatin (low dose  $\leq 20$ mg/day and a high dose group  $\leq 80$  mg/day) on changes in LID. Secondary outcomes will include examination for treatment group differences in changes in Parkinsonism (tapping AUC, UPDRS III, Hoehn and Yahr, Schwab and England, PDQ-39) including pERK1/2 levels following the previously described methods. Should violations of normal regression assumptions be found, either outcome transformations or alternative regression distributions (e.g. negative binomial to account for positive skew) will be applied as necessary. Sub analyses will examine co-morbidity rates between the groups.

Additionally, pERK1/2 levels will be examined. Initial analysis will examine the relationship between severity of dyskinesia (with the AUC of the RMSV) and pERK1/2 levels using correlations. Further analysis will examine if pERK1/2 levels vary by cohort using ANOVAs and multiple regression techniques. Assessment of confounders of the relationship between pERK1/2 and dyskinesia severity will be examined.

**Sample Size:** Based on results of a validation study of dyskinesia scales [35], using a one-way ANOVA to examine the difference in part 3, impairment, of the Unified Dyskinesia Rating Scale (UDysRS) between the three pairwise comparisons, 37 participants are needed in each group to detect a moderate effect size ( $f=0.30$ , at least one group difference of 3.75 points) with a significance of 0.05 and power of 0.80. Pairwise comparison of statin before levodopa versus no statin will receive priority. To account for drop outs, an additional 3 participants will be included in each of the groups. Additional 10 will be included for screen failures (total 130). Total enrollment will be 40 per group, 120 total. See Table 5 for estimated recruitment goals.

*Table 5. Estimated Recruitment Totals per Site*

	VAPORHCS	VAPUGHCS	OHSU	Total
Recruitment	60	28	32	120

*Figure 1. Recruitment Goals over time*

Subjects were described previously and in the first cohort will be those who had been on a statin first and remained on it while they were initiated on LD. The second cohort will be those who started a statin AFTER beginning LD. The third cohort will be subjects with no history of statin intake. Matching will occur based on gender, severity of disease based on a PD rating scale, and LD dose

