### Research Design and Methods

**Overview:** This study is a retrospective three cohort design and will compare statin exposure BEFORE beginning LD, *versus* statin exposure AFTER LD is begun, *versus* NO statin exposure in PD subjects who

are matched for disease characteristics (severity), gender, and total LD exposure. The primary endpoint is the severity of LID between the groups after years of opportunity to develop LID. The power of the VA database is its ability to identify the subjects appropriate for our three cohorts. Dyskinesia amplitude will be measured repeatedly over a single intravenous levodopa cycle, generating an area under the curve (AUC) for each subject, leading to a group AUC for each cohort. All dyskinesia ratings will be by a blinded rater. We will be able to determine whether a statin reduces eventual LID in Veterans who take levodopa for PD, an important public health problem that causes quality of life reduction and raises health care costs for the Veterans Health Administration.

[figure not shown]
**Primary Endpoint:** Difference between cohorts in peak Unified Dyskinesia Rating Scale

**Secondary Endpoints:** Difference between cohorts in AUC of RMSV-AP through levodopa cycle, AUC mAIMS of LID through levodopa cycle

**Tertiary Endpoints:** QoL scales (PDQ-39, PDys-26,) and ERK1/2 levels as correlated with AUC RMSV – AP through levodopa cycle in subjects

**Rationale for study population:** We will generate three retrospective cohorts: (Cohort A) Statin Exposure before LD, (Cohort B) Statin Exposure after LD, and (Cohort C) No statin exposure (or LD only). See Figure F.

*Figure G. Study Design.*

We will also perform a subgroup analysis comparing simvastatin  $\leq 20$ mg/day (low dose) and a high dose group  $\leq 80$  mg/day.

**Rationale for Dyskinesia endpoints:** We are measuring LID with (A) Unified Dyskinesia Rating Scale, (B) Force Plate, and (C) Subjective Measures.

A. Unified Dyskinesia Rating Scale (UDysRS): The Movement Disorders Society has adopted this scale as the recommended primary measurement tool for dyskinesia. It was determined be best amongst many existing scales to detect changes in dyskinesia using a known treatment that reduces LID severity[24].

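### The 0.80 power at 37 per group is for UDysRS Part 3, not for the declared primary (peak UDysRS total), whose peak is not fully defined and which the Design section replaces with group AUCs

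*Combined protocol and SAP*

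**What the plan says.** **Primary outcome.** The endpoint list under Research Design and Methods gives the primary endpoint as "Difference between cohorts in peak Unified Dyskinesia Rating Scale", without saying whether a part or the total is meant. The Data Analysis section settles that: "The peak UDysRS total score will be used as the primary outcome measurement for LID as it is the accepted gold standard". The UDysRS entry under Dyskinesia Measurements forms the total by adding the historical parts (1 and 2) to the objective parts (3 and 4).

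**AUCs.** The endpoint list makes these secondary: "Difference between cohorts in AUC of RMSV-AP through levodopa cycle, AUC mAIMS of LID through levodopa cycle". Data Analysis calls them additional outcome measurements, while describing the AUC approach as the more sensitive and precise one.

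**Design section (Methods).** This names LID severity as the main outcome. It then specifies that each subject's LID is represented by an AUC from the test day and that the group AUCs of the three cohorts will be compared. It does not mention the UDysRS.

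**Sample size.** A one-way ANOVA is used to "examine the difference in part 3, impairment, of the Unified Dyskinesia Rating Scale (UDysRS"), and "37 participants are needed in each group to detect a moderate effect size" (f = 0.30, at least one group difference of 3.75 points, significance 0.05, power 0.80). The statin-before-levodopa versus no-statin comparison is given priority. Three participants per group are added for dropout, making 40 per group.

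**Analysis model.** The primary analysis is per protocol, "using ordinary least-squares (OLS) regression to examine the difference between the groups" with adjustment for covariates.

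**Collection.** Table 3 lists UDysRS Parts 1 and 2 among the questionnaires completed at home. Table 4 schedules Parts 3 and 4 at 9:00, at 11:00 and at the last rating of the day.

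**The concern.** A power statement supports a trial's size only for the variable it was computed on. Here it was computed on one part of a four-part score, while the sum of all four parts decides the study. The other three parts can change both the between-group difference and the SD, so f = 0.30 on Part 3 does not carry over to the total without a stated reason. A reader who takes 0.80 as the power for the primary outcome is relying on something the plan does not say.

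Two further gaps concern that same variable. A reader who starts from the Design section would take the group AUC comparison as the main result. And two analysts given the same ratings could compute different peak totals. If the total-score and AUC results differed, or if the two versions of the peak did, the protocol should already have settled which one counts.

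**Working it through.** **1. Reproduce the stated figure (Part 3).**
Inputs from Sample Size: k = 3 groups, f = 0.30, alpha = 0.05, target power 0.80.
Omnibus F test with df = (k − 1, N − k) and noncentrality λ = f² × N.

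- n = 37: N = 111, df = (2, 108), λ = 0.09 × 111 = 9.99, power 0.803.
- n = 36: N = 108, df = (2, 105), λ = 0.09 × 108 = 9.72, power 0.792.

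So 37 is the smallest n per group that reaches 0.80. The arithmetic is correct for Part 3. If all 40 per group are evaluable, power is 0.836.

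**2. What those inputs imply for Part 3.**
The SD is not stated, but f and the 3.75 points determine it once a pattern of means is assumed.

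- Third group midway: f = d/√6, so d = 0.30 × √6 = 0.735 and SD = 3.75/0.735 = 5.10.
- One group differs from two equal groups: f = d × √2/3, so d = 0.30 × 3/√2 = 0.636 and SD = 3.75/0.636 = 5.89.

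**3. The prioritised contrast, still on Part 3.**
Two-sided t test at 0.05, 37 per group, noncentrality d × √(37/2), assuming statin-before and no-statin are the two groups that differ by 3.75 points.

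- d = 0.735: noncentrality 3.16, power 0.88.
- d = 0.636: noncentrality 2.74, power 0.77.

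The omnibus 0.80 is therefore not the power of this contrast either, although it lies between the two values.

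**4. The declared primary (peak total).**
The documents give no SD, difference or f for the total, so no single figure can be computed. The table uses assumed values of f, the same omnibus test and no covariates.

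| f on the total (assumed) | λ at N = 111 | Power at 37 per group | n per group for 0.80 |
|---|---|---|---|
| 0.20 | 4.44 | 0.44 | 82 |
| 0.25 | 6.94 | 0.64 | 53 |
| 0.30 | 9.99 | 0.80 | 37 |
| 0.35 | 13.60 | 0.91 | 28 |

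The stated power carries over only if f on the total is also about 0.30, that is, if the group difference grows in the same proportion as the SD when Parts 1, 2 and 4 are added. The plan neither makes nor sources that assumption. The planned covariate-adjusted regression could have higher or lower power than these unadjusted figures.

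**5. Which outcome is primary.**

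| Place | Primary or main outcome | AUCs |
|---|---|---|
| Endpoint list | Peak UDysRS (part or total not specified) | Secondary |
| Data Analysis | Peak UDysRS total | Additional |
| Design (Methods) | LID severity, specified as group AUCs | Main |

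Two formal statements agree. The Design section stands alone against them.

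**6. What the peak of the total is.**
Write H for the single Parts 1 + 2 questionnaire score, and P3(t), P4(t) for the ratings at the three scheduled times. Two readings fit the text:

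- same-time: H + max over t of [P3(t) + P4(t)];
- separate: H + max over t of P3(t) + max over t of P4(t).

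The second is never smaller than the first. It is larger whenever no single rating time attains both maxima.

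**The case against.** The strongest reply is that the primary outcome is not really in doubt. The labelled endpoint list and Data Analysis both make peak UDysRS primary and both put the AUCs below it. That stands, and it reduces the AUC conflict to one unreconciled paragraph in the Design section.

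Several stronger readings are tempting, and the documents do not support them:

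- **That the Overview also makes an AUC primary.** It says "The primary endpoint is the severity of LID between the groups after years of opportunity to develop LID" and later describes cycle measurements "generating an area under the curve (AUC) for each subject, leading to a group AUC for each cohort". The second statement describes how dyskinesia amplitude is measured; it does not assign endpoint status. Likewise, the two main measurements named under Dyskinesia Measurements are instruments.
- **That the trial is underpowered for the total.** The f values in the table are assumptions, and the upper one gives 0.91. The Anticipated Results section expects the dyskinesia outcomes to correlate. This does not establish f = 0.30 for the total, but neither does anything in the plan show a smaller f.
- **That Part 3 is a poor guide because it covers 28 of the 100 summed points.** That is a share of range, not of variance, and says nothing about power.
- **That the stated total range (0 to 104, against 44 + 12 + 28 + 16 = 100) affects the analysis.** The score is a sum of items; the discrepancy is clerical.

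It is also fair to say that the peak has a natural reading, namely the questionnaire score plus the highest test-day score. What remains open is whether the Part 3 and Part 4 maxima must come from the same rating time.

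**Conclusion.** The point holds as a mismatch that should be fixed. The 37 per group is correctly computed, but for Part 3. The 0.80 power does not describe the declared primary, for which power is unsupported and not shown to be lower. The 0.44 to 0.91 range rests on assumed f from 0.20 to 0.35, the unadjusted omnibus test and 37 evaluable per group. The 0.77 to 0.88 for the prioritised contrast is for Part 3 only and assumes that those two groups are the ones differing by 3.75 points. The Design section contradicts two formal statements of the primary outcome, and the definition of the peak leaves at least two versions of the primary variable open.

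**What to change.** 1. **Sample Size.** State that 0.80 power at 37 per group applies to Part 3. Then either justify an effect size for the peak total with a sourced SD and difference, or report power over an assumed range of f (0.20, 0.25, 0.30, 0.35), labelled as unadjusted, together with power for the statin-before versus no-statin contrast. Alternatively, the sponsor may name peak Part 3 as primary, which matches the existing calculation; Data Analysis and the endpoint list would then have to say so.
2. **Design.** Name the same primary outcome as the endpoint list and Data Analysis, with the AUCs secondary.
3. **Data Analysis.** If the total stays primary, define its peak as the Parts 1 + 2 score plus the largest same-time Parts 3 + 4 score across the scheduled ratings. Report Part 3, the variable the trial was sized on, as a prespecified supporting analysis.

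The stated total range can be corrected in the same amendment.

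Cost: a text amendment and, if the total stays primary, one supporting analysis of data already collected. No visits, ratings or participants are added. The only outside input is an SD and difference for the total, needed only if the sponsor chooses to justify a single effect size.

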### Specific Aims

**Aim 1. Statin Use & LID Development:** Determine if statin use coincident (prior) to LD initiation reduced LID development compared with no statin use or late statin use using a retrospective cohort design.

*Hypothesis 1:* HMG-CoA reductase inhibition by statin interrupts the molecular signaling changes induced by LD in the earliest period of exposure associated with "priming" for LID.

**Aim 2 Statin Use & LID Severity:** Determine if statin use after LD is initiated reduced LID development (severity) over time compared with no statin use using a retrospective cohort design.

*Hypothesis 2:* HMG-CoA reductase inhibition by a statin can still be effective in reducing the development of progression of dyskinesia even if started after priming processes are established.

**Aim 3 LID and pERK1/2:** Determine levels of phosphorylated ERK1/2 levels in CD3/CD20 lymphocytes and compare them with dyskinesia severity.

*Hypothesis 3:* Dyskinesia severity correlates with phosphorylated ERK1/2 levels and may associate as a dyskinesia biomarker.

**Aim 4 LID Measurement:** Compare the dyskinesia measurements between the force plate, the inertial sensors, the Unified Dyskinesia Rating Scale (UDysRS), and the Modified Abnormal Involuntary Movement Scale (mAIMS).

*Hypothesis 4:* The force plate is a valid and reliable method of measuring dyskinesia when compared to the gold standard (mAIMS), a patient/clinician impression of dyskinesia (UDysRS), and a novel form of dyskinesia measurement (the inertial sensors).

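### The stated 37 per group and power of 0.80 belong to the omnibus ANOVA, not to the three pairwise comparisons the sentence names, and the priority given to statin-before versus no statin has no testing rule

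*Combined protocol and SAP*

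**What the plan says.** The Sample Size paragraph under Data Analysis plans a one-way ANOVA on part 3 (impairment) of the UDysRS and says that "between the three pairwise comparisons, 37 participants are needed in each group to detect a moderate effect size". The effect is f=0.30, glossed as "at least one group difference of 3.75 points", with significance 0.05 and power 0.80. Three per group are added for drop-outs, giving 40 per group and 120 in all. The paragraph then says: "Pairwise comparison of statin before levodopa versus no statin will receive priority".

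The Specific Aims are framed as contrasts between cohorts. Aim 1 asks whether an early statin "reduced LID development compared with no statin use or late statin use", which is A-C and A-B. Aim 2 is B-C: "Determine if statin use after LD is initiated reduced LID development (severity) over time compared with no statin use". It has its own hypothesis, that a statin "can still be effective in reducing the development of progression of dyskinesia even if started after priming processes are established". Anticipated Results expects B to do better than C but less well than A, and does not say by how much.

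The primary analysis under Data Analysis is on the peak UDysRS total, "using ordinary least-squares (OLS) regression to examine the difference between the groups" with adjustment for covariates. Neither that text nor the Sample Size paragraph gives an order, gate, alpha split or multiplicity adjustment for the pairs.

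**The concern.** The sentence mixes two things. ANOVA, f and the gloss on f describe a single two-degree-of-freedom test of any difference among three groups. The phrase about pairwise comparisons describes three separate tests. A reader can therefore take 0.80 as the power of each pair.

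That matters most for Aim 2 and for the A-B half of Aim 1. If B-C is believed to have 80% power, a non-significant result invites the conclusion that starting a statin late does not help, when the test may have had little chance of showing a benefit of the expected size. Separately, if priority is not turned into a rule, the way the three pairs are tested, and so the family-wise error, can be settled after the data are seen.

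**Working it through.** **Inputs.** From the Sample Size paragraph: three equal groups, 37 per group, f=0.30, alpha 0.05. From Anticipated Results: B lies between C and A. Assumed, because the documents are silent: two-sided pairwise tests, pooled error variance (111 − 3 = 108 df), and B's exact position.

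**Step 1: the plan's own figure.** Omnibus F test, noncentrality λ = N·f², with 2 and N − 3 df.
- n=36: λ = 108 × 0.09 = 9.72, power 0.792
- n=37: λ = 111 × 0.09 = 9.99, power 0.8035

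So 37 is the smallest group size reaching 0.80 for the omnibus test. The figure reproduces.

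**Step 2: pairwise power at the same f and n.** In SD units of benefit, let C=0, A=D and B=tD, where t is the fraction of A's benefit that B has. Then f = D·√[2(1 − t + t²)/9]. Setting f=0.30 gives D = 0.30/√[2(1 − t + t²)/9]. The standardised differences are D for A-C, tD for B-C and (1 − t)D for A-B. Power comes from the noncentral t distribution with noncentrality (difference) × √(37/2) and 108 df.

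| t | D | A-C | B-C | A-B |
|---|---|---|---|---|
| 0 | 0.636 | 0.77 | null | 0.77 |
| 0.25 | 0.706 | 0.85 | 0.12 | 0.62 |
| 0.50 | 0.735 | 0.88 | 0.35 | 0.35 |
| 0.75 | 0.706 | 0.85 | 0.62 | 0.12 |
| 1 | 0.636 | 0.77 | 0.77 | null |

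The rows at 0.25, 0.50 and 0.75 illustrate an assumption. Over a grid of 1,001 values of t from 0 to 1, A-C runs from 0.774 to 0.880, B-C and A-B each peak at 0.774, and the weaker of B-C and A-B peaks at 0.347, at t=0.5.

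**Step 3: relaxing the conditions.** For covariate adjustment, divide the differences by √(1 − R²) and remove seven df for the covariates named in Data Analysis; no variance inflation is applied. R² is an assumption.

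| Analysable per group | R² | B-C reaches 0.80 from t of | A-B there |
|---|---|---|---|
| 40 | 0 (unadjusted) | 0.99 | 0.05 |
| 37 | 0.3 | 0.79 | 0.12 |
| 40 | 0.3 | 0.75 | 0.16 |
| 37 | 0.4 | about 0.71 | 0.20 |

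Correlation between cohort and covariates works the other way. With R² of 0.1 and a variance inflation of 1.1, B-C does not reach 0.80 at any t. If A-C is instead fixed at 3.75 points with the SD implied by B midway (3.75/0.735 = 5.10), B-C reaches 0.80 from about t=0.90, where f has risen to 0.33 and A-B is 0.06.

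**Step 4: family-wise error over the three pairs, no true difference, by simulation.**
- all three tested at 0.05 with no gate: 12.2%
- pairs tested only after a significant omnibus test: 5.0%
- B-C and A-B tested only after a significant A-C: 5.0%

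Both gates also hold when only one null is true. With three groups, once one pair truly differs, at most one of the other two nulls can be true, and it is tested at 0.05.

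**The case against.** The strongest reply is that nothing has been miscalculated. A one-way ANOVA, f and the gloss about one group difference all identify the omnibus test, and the paragraph never says in terms that each pair has 0.80. That stands: this is a wording fault in one phrase, and the sample size is not in error. It does not remove the fault, because the phrase names the pairs and the next sentence turns to one of them.

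Next, the plan names A-C as its lead contrast, and that contrast has 0.77 to 0.88, so the main question is reasonably served. Lower power for B-C also follows from the sponsor's own expectation of a smaller effect in B. Both points stand, and they are reasons to state the pairwise power.

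Third, the 25% to 75% positions appear nowhere in the documents, and neither does two-sidedness for the pairs. One-sided tests at 0.05 would give B-C 0.19, 0.47 and 0.73 at the three positions. This stands as a limit on the illustration; those values are still below 0.80.

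A reader might infer that Aim 2 cannot reach 80% power. The documents do not support that: with adjustment or more analysable patients B-C can pass 0.80 when B has most of A's benefit, and they give no R² from which to set a limit. A reader might also infer that the trial will run at 12% family-wise error. That does not follow either: the figure applies only if all three pairs are tested ungated at 0.05 and no cohort differs, and the OLS description leaves room for a group test first. What is missing is a statement of which.

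**Conclusion.** The point holds as a labelling fault and a missing rule. The 0.80 is the unadjusted omnibus power for UDysRS part 3. It is not the power of each pair, nor of the covariate-adjusted OLS on the peak UDysRS total.

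At f=0.30 and 37 per group, unadjusted, two-sided 0.05, with B between C and A, neither B-C nor A-B exceeds 0.77, and at least one of them is at or below 0.35 wherever B lies. Only the position-specific values (B-C 0.12, 0.35, 0.62 and A-B 0.62, 0.35, 0.12) rest on the assumed 25%, 50% and 75%. Outside those conditions, in the cases tabulated, B-C reaches 0.80 only when B has roughly 70% or more of A's benefit, and A-B is then about 0.20 or less. Because R² is unknown, that is not a general bound.

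The priority given to A-C has no stated operation, so family-wise error is undetermined: about 12% under the complete null if all pairs are tested at 0.05, and 5% under either gate examined. The plan should be corrected before analysis; N need not change.

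**What to change.** Keep N and change the text.

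1. State that 0.80 is the unadjusted omnibus power for UDysRS part 3, and that it is not the power of each pair or of the adjusted OLS on the peak UDysRS total.
2. Add the pairwise power, labelled as unadjusted part 3, with B's position labelled as an assumption: for B at 25%, 50% and 75% of A's benefit, A-C 0.85, 0.88, 0.85; B-C 0.12, 0.35, 0.62; A-B 0.62, 0.35, 0.12.
3. Before analysis, replace the priority sentence with one rule that controls error over the three pairs on the primary outcome. The sponsor can choose between:
   - (a) a significant 2-df group test in the primary model, then each pair at 0.05. This matches the sizing and does not place Aim 2 behind A-C;
   - (b) A-C first at 0.05, then B-C and A-B each at 0.05 only if A-C is significant. This gives priority a literal meaning.
4. Report B-C and A-B with 95% confidence intervals, and do not read non-significance as no effect.

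**Cost.** No extra patients. The stated power for B-C and A-B becomes less favourable, and each gate costs some power (B at 25%, 50%, 75%). Under (a), A-C falls to 0.78, 0.80, 0.78 and B-C to 0.12, 0.34, 0.59. Under (b), A-C is unchanged and B-C becomes 0.11, 0.34, 0.57; because A-C misses in 1 − 0.88 to 1 − 0.85 of trials, Aim 2 goes untested in 12% to 15% of them.
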